**Study end-points:**

***Primary end-point***

- i. Time to vasopressor independence. Defined as the time from starting the active treatment/placebo to discontinuation of all pressors
- ii. Delta SOFA score, defined as the initial SOFA score minus the day 4 SOFA score

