***Secondary end-points***

- iii. 28-day mortality
- iv. Hospital mortality
- v. PCT clearance (PCT-c) calculated using the following formula: initial PCT minus PCT at 96 hours, divided by the initial PCT multiplied by 100. [67,68]
- vi. ICU mortality
- vii. ICU length of stay (LOS) and ICU free days. ICU free days is calculated as the number of days alive and out of the ICU to day 28
- viii. Hospital LOS

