**Power Calculation:**

Based on the results of the preliminary study of Marik et al we project that the combination of hydrocortisone, vitamin C and thiamine could reduce time to vasopressor discontinuation from 54 (+/- 30 hours) versus 30 hours. For the additional primary outcome we projected a greater change of SOFA score of 4 (+/- 3) versus 2. Assuming a type 1 error of 5% (alpha of 0.05) and a power of 80% (the ability to detect a difference between two groups when a difference exists) would require a sample size of 94 patients. To account for dropouts and patients not requiring vasopressor therapy we will therefore aim for a sample size of 140 patients.

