***Data Collection:***

The following de-identified demographic and clinical data will be collected.

- i. Age
- ii. Sex
- iii. Weight
- iv. Admitting diagnosis and possible site of infection
- v. Blood culture results
- vi. Co-morbidities, including diabetes, hypertension, cardiac failure, COPD, malignancy
- vii. Requirement for mechanical ventilation (Y/N).
- viii. Use of vasopressor agents (Y/N). The hourly dosage of vasopressors will be recorded as the norepinephrine equivalent dosage. [70,71]
- ix. Duration of vasopressor use
- x. Time to vasopressor independence from start of active drug/placebo
- xi. Daily urine output (for first 4 days)

xii. Fluid balance after 24 and 72 hours

xiii. Presence of acute kidney injury (AKI). Presence of AKI: Acute kidney injury (AKI) will be defined using the KDIGO criteria; namely, an increase of the s-creatinine > 0.3 mg/dl or a level > 1.5 times the baseline value. [27] If the baseline s-creatinine is not known a value > 1.5 mg/dl will be regarded as diagnostic of AKI.

xiv. Length of ICU and hospital stay

xv. ICU, hospital, and 28-day mortality

xvi. Routine laboratory data for 4 days including:

a. serum creatinine

b. white cell count (WBC)

c. platelet count

d. total bilirubin

e. PaO2/FiO2 ratio

f. Procalcitonin (PCT) – on days 1 and 4

g. lactate level

h. urine oxalate level (day 4)

xvii. HostDx Sepsis genetic testing (day 1) if consent is provided for additional sub-study.

xviii. The patients' admission APACHE II and APACHE IV scores will be recorded. The APACHE IV score allows calculation of the predicted hospital mortality and predicted ICU length of stay (LOS).

ix. The daily SOFA (Sepsis-related Organ Failure Assessment) score will be recorded for the first 4 treatment days.

The APACHE II score (incrementing score of 0-71) and APACHE IV score (incrementing score 0-286) are standardized measures of disease severity that are used to predict hospital mortality and ICU LOS.

[72,73] The SOFA score was designed to sequentially assess the severity of organ dysfunction in patients who are critically ill from sepsis (incrementing score 0-24). [74]. The SOFA scores is calculated 24 hours

after admission to the ICU and daily thereafter. SOFA scores that increase by about 30 percent are associated with a mortality of at least 50 percent.[75]

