Data will be collected in the attached Excel spreadsheet (Appendix A – Sepsis Data spreadsheet). No personal identifiers will be recorded on the spreadsheet. We will not be recording names, dates of birth, social security or EMR numbers or any other HPI data in the data collection spreadsheet. Each record will be assigned a unique study ID number (subject ID key). A separate password protected spreadsheet will have a list of subject ID number and the corresponding medical record numbers (Subject ID Key data sheet). This spreadsheet will only be accessible to the principle investigator and sub-PI. The pharmacist will have a copy of the “Research Randomization and Dispensing Log” with an additional field which will include the randomization code to active vitamin protocol or placebo. Only the pharmacist will have access to the “Research Randomization and Dispensing Log” until after the study is completed, when it will be made available to the principle investigator and sub-PI.

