***Data analysis:***

Summary statistics will be used to describe the clinical data and presented as mean  $\pm$  SD, median with interquartile range (IQR) or percentages as appropriate. Chi squared analysis with Fisher’s exact test (when appropriate) and Student’s t test (Mann Whiney U test for non- normal distributions) were used to compare data between the active treatment group and the placebo group with statistical significance declared for probability values of 0.05 or less.

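### No rule for death in the primary end-points: read literally, a death on vasopressors scores as early vasopressor independence

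*Protocol*

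**What the plan says.** Both documents list two primary end-points in identical words.

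- Time to vasopressor independence: "Defined as the time from starting the active treatment/placebo to discontinuation of all pressors". The Protocol's Data Collection list repeats the variable as "Time to vasopressor independence from start of active drug/placebo", again with no rule for a patient who dies.
- "Delta SOFA score, defined as the initial SOFA score minus the day 4 SOFA score". No value is assigned to a patient who has died by day 4. Data Collection says SOFA is scored "after admission to the ICU and daily thereafter", and recorded for the first 4 treatment days.

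Survival is written into one secondary end-point: "ICU free days is calculated as the number of days alive and out of the ICU to day 28".

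For continuous outcomes the Data analysis section names Student's "t test (Mann Whiney U test for non- normal distributions"). It gives no censoring, competing-risk, worst-rank or missing-data rule. The Power Calculation explains its inflation thus: "To account for dropouts and patients not requiring vasopressor therapy we will therefore aim for a sample size of 140 patients". Deaths are not mentioned. The allocation log stays with the pharmacist "until after the study is completed, when it will be made available to the principle investigator and sub-PI".

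**The concern.** Death ends every infusion. An end-point that stops the clock when vasopressors stop, with no condition of being alive, lets the worst outcome be recorded as a short time, which is a good result. The name of the end-point suggests a living patient, but the definition does not say so.

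Whoever analyses the data must therefore count such deaths as discontinuation, drop them or rank them worst, and neither document chooses. Two things are at stake. Under the literal reading, an imbalance in deaths on vasopressors moves the primary comparison towards the arm with more deaths. And if the choice stays open until results are seen, the type 1 error rises even when deaths are balanced. The separate mortality end-points would reveal an imbalance but would not correct the primary test.

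**Working it through.** **Inputs from the Power Calculation.** 54 h (SD 30) v 30 h for vasopressor time; delta SOFA 4 (SD 3) v 2; alpha 0.05; power 80%; 94 patients, raised to 140.

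**Assumptions not in the documents.** 1:1 allocation (47 per arm); two-sided tests; SD 30 h in both arms, although the plan attaches it only to the 54 h arm; gamma-distributed times; the share of patients dying on vasopressors and the timing of those deaths.

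**1. The plan's own figure.** n per arm = 2(1.960 + 0.842)²(SD/difference)².
- Vasopressor time: 2 × 7.85 × (30/24)² = 24.5, so 25 per arm, 50 in total (52 with the t distribution).
- Delta SOFA: 2 × 7.85 × (3/2)² = 35.3, so 36 per arm, 72 in total (74 with t).

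The stated 94 is not reproduced and is larger than either. That is a separate matter; 47 per arm is used below only because it is the plan's number.

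**2. Literal scoring.** A death on vasopressors at 24 h scores 24 h, which is better than the 30 h projected for the active arm.

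**3. Mean shift, death counted as discontinuation at 24 h.** Arm mean = (1 − d) × weaning mean + d × 24, where d is the proportion dying on vasopressors.
- No effect, 10% active v 20% placebo: 0.9×54 + 0.1×24 = 51.0 v 0.8×54 + 0.2×24 = 48.0, so 3 h in favour of placebo.
- Planned effect, same deaths: 0.9×30 + 0.1×24 = 29.4 v 48.0, so 18.6 h instead of 24.
- Planned effect, 10% v 30%: 29.4 v 0.7×54 + 0.3×24 = 45.0, so 15.6 h.

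**4. Simulation, 47 per arm** (Mann-Whitney unless stated; deaths are active v placebo).

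| Scenario | Result |
|---|---|
| No effect, equal deaths 5–20%, death as discontinuation fixed in advance | 2.2–2.7% each way (nominal 2.5%) |
| No effect, 10% v 20%, death as discontinuation | placebo wrongly favoured: about 11% (mean death time 12 h), 7–8% (24 h) |
| Half the planned effect (54 v 42 h), 10% v 20%, 24 h | active superior: 28–30% (death as discontinuation), 55% (dropped), 71% (ranked worst) |
| No effect, equal deaths 10–20%, best of the three rules picked afterwards | about 9–12% two-sided (nominal 5%) |
| Planned effect, no deaths | power 99.6% (t test 96%) |
| Planned effect, 10% v 20%, death as discontinuation | t-test power 76–79% (12 h), 82–86% (24 h) |
| Planned effect, 10% v 30%, death as discontinuation | t-test power about 55% (12 h), 69% (24 h); Mann-Whitney 64% (12 h) |

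In the third row the 71% partly reflects the mortality difference itself.

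**5. Delta SOFA, survivors only.** If death risk and worsening have correlation r, the survivors' mean shifts by r × SD × φ(z)/(1 − p), where p is the proportion dying before day 4 and z the matching normal quantile. The factor φ(z)/(1 − p) is 0.060, 0.109 and 0.195 at p = 2.5%, 5% and 10%. A true difference of 2.0 then reads:
- 2.5% active v 5% placebo: 2.0 − r×3×(0.109 − 0.060) = 1.96 (r = 0.3) to 1.90 (r = 0.7).
- 5% v 10%: 2.0 − r×3×(0.195 − 0.109) = 1.92 to 1.82.

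The loss is 0.04–0.18 points, towards no effect, and nil at r = 0.

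**The case against.** The best defence has four parts.

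*Independence means a living patient.* That is the natural sense, and a careful analyst might apply it. It excludes one rule but still leaves open whether a death is dropped, censored or ranked worst.

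*Deaths on vasopressors may be few.* Care-limited and terminal patients are excluded. The mortality cited in the Background (about 25% in sepsis, up to 45% in septic shock) covers all deaths. In the preliminary before-after study every treated patient was weaned, yet 4 of 47 died. This stands: the 5–30% used here is assumed. A reader might put that study's hospital mortality (8.5% v 40.4%) straight into the calculation, but this would treat every hospital death as a death on vasopressors, which its own report contradicts.

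*The allocation log is withheld until completion, so a rule can still be set blind.* True, but nothing in the plan requires it.

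*Ranking deaths worst changes the question and can cost power.* Also true. Any single rule fixed in advance removes the open choice; worst rank is a preference with a price, set out under the fix.

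**Conclusion.** The omission is plain in both documents, and confidence in it is high. Confidence in the size is moderate, because it rests on assumed death rates and times, a common SD of 30 h and 1:1 allocation. In the scenarios above, the unwritten rule moves the chance of a positive primary result at half the planned effect from about 30% to about 71%. Leaving the rule open roughly doubles the two-sided false-positive rate.

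Three stronger readings are not supported.

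- A reader might infer that the plan scores deaths as successes, or is tilted towards active treatment. The wording permits that scoring but does not require it. Wrongly favouring active would need more deaths on vasopressors in the active arm, the opposite of the mortality direction in the preliminary study. In that study's direction, the literal reading understates benefit.
- A reader might infer a general loss of power. It depends on the imbalance: at 10% v 20% deaths the t test falls below 80% only with the earlier deaths, whereas at 10% v 30% the loss is large at both 12 h and 24 h.
- A reader might infer that delta SOFA is seriously biased, or that the plan says to drop deaths from it. No text says so. Exclusion is simply what happens by default when no day-4 score exists, and the resulting bias is small. This part is secondary.

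**What to change.** State in the SAP, before the randomisation log is released:

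1. Independence counts only if the patient is alive and off all vasopressors. A death on vasopressors is never scored as discontinuation.
2. The primary test is Mann-Whitney, which the plan already names, with deaths before independence ranked worst and tied. A deaths-excluded analysis and a cumulative incidence analysis with death as a competing event are sensitivity analyses.
3. One rule for delta SOFA is fixed in advance, for example deaths before day 4 ranked worst, with survivors only as sensitivity.
4. Deaths on vasopressors and deaths before day 4 are reported by arm.

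The work is SAP wording and a few lines of code. Hourly vasopressor dose and mortality are already collected; date and hour of death should be added.

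The statistical price is that the end-point becomes a composite with death. With the planned effect and equal deaths on vasopressors, worst-rank power is about 95% at 10% deaths and 80% at 20%. At 20%, death as discontinuation or dropping deaths would keep about 95–98%.

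How long a patient must stay off vasopressors, and how day-4 SOFA is handled in patients discharged alive, are separate questions and not part of this change.

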# **Outcomes of Metabolic Resuscitation Using Ascorbic Acid, Thiamine, and Glucocorticoids in the Early Treatment of Sepsis.**

## **ORANGES Trial**

**NCT#: NCT03422159**

### **Background and Significance:**

The global burden of sepsis is substantial with an estimated 15 to 19 million cases per year; the vast majority of these cases occur in low income countries. [1] With more timely diagnosis and improvement in supportive care the 28-day mortality from sepsis in high income countries has declined to about 25%, however, the mortality from septic shock remains as high as 45%. [2,3] Moreover, the mortality from sepsis and septic shock in low income countries is reported to be as high as 60%. [4-6] In addition to short term mortality, septic patients suffer from a numerous short- and long-term complications and are at an increased risk of death for up to five years following the acute event. [7] Over the last 3 decades over 100 phase II and phase III clinical trial have been performed testing various novel pharmacologic agents and therapeutic intervention in an attempt to improve the outcome of patients with sepsis and septic shock; all of these studies have failed to show an improvement in patient outcomes. [8] New therapeutic approaches to sepsis are desperately required; considering the global burden of sepsis these interventions should be effective, cheap, safe and readily available.

A large body of experimental data has demonstrated that both corticosteroids and intravenous vitamin C reduce activation of nuclear factor KB (NFKB) attenuating the release of pro-inflammatory mediators, reduce the endothelial injury characteristic of sepsis thereby reducing endothelial permeability and improving macrocirculatory flow, augment the release of endogenous catecholamines and enhance vasopressor responsiveness. [9-16] In animal models these effects have resulted in reduced organ injury and increased survival. Corticosteroids have been evaluated in several clinical trials, with meta-analysis of these trials demonstrating somewhat conflicting outcomes. [17-20] Low-dose stress corticosteroids have proven to be safe with no increased risk of clinically important complications. [17] While corticosteroids decrease vasopressor dependency the effect on survival is less clear. [19,21]

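### Primary end-point i does not say which vasopressor stop counts, for how long, or whether the patient must be alive, so the estimate can be biased in either direction

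*Protocol*

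**What the plan says.** The protocol (Primary end-point) names the first primary end-point "Time to vasopressor independence" and defines it in one clause: "Defined as the time from starting the active treatment/placebo to discontinuation of all pressors". The SAP (Study end-points) has the same definition and adds no derivation rule.

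The protocol's Data Collection list has three related items. The time from study drug to independence is one and "Duration of vasopressor use" is another; neither comes with a rule for restarts. The third is the dose record: "The hourly dosage of vasopressors will be recorded as the norepinephrine equivalent dosage". No recording window is given for it, although several other items in the list are limited to the first 4 days.

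The Power Calculation assumes the combination "could reduce time to vasopressor discontinuation from 54 (+/- 30 hours) versus 30 hours". The Data analysis section, the same in both documents, offers Student's t test, or the Mann-Whitney U test when the distribution is not normal. It gives no rule for a patient who never comes off pressors or who dies on them.

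**The concern.** Three choices are left open on a primary end-point: first or final stop, how long the patient must stay off, and whether the patient must be alive. From the same hourly record, a patient who stops for an hour and then needs two more days of support could be given either of two very different times. A patient whose pressors are stopped at death could be recorded as having become independent.

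Two things are at stake. If restarts or deaths on pressors differ between arms, the literal rule can create or hide a difference. And if the choice is made after allocation is released, it is a free analytic choice on the outcome that carries the trial's claim.

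**Working it through.** **1. The plan's own figure.** Inputs from the Power Calculation: 54 vs 30 h, SD 30 h; "we projected a greater change of SOFA score of 4 (+/- 3) versus 2"; alpha 0.05; power 80%. Two-sided testing and 1:1 allocation are not stated and are assumed. Per arm, n = 2(1.96 + 0.842)² × SD²/difference², with (1.96 + 0.842)² = 7.85.

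- Vasopressor time: 2 × 7.85 × (30/24)² = 24.5, so 25 per arm, 50 in total.
- Delta SOFA: 2 × 7.85 × (3/2)² = 35.3, so 36 per arm, 72 in total.

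Neither gives the stated 94. That is a separate sample-size matter and does not depend on the restart rule. Below, 94/2 = 47 per arm serves only as a working size.

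**2. Restarts when the planned effect is real.** The documents give no restart rate. Assumptions: final-stop means 30 h (active) and 54 h (placebo); a share r of each arm restarts; a restarter's first stop comes at half the final time. Then

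first-stop difference = 54(1 − 0.5 r_placebo) − 30(1 − 0.5 r_active).

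| Restart share, active / placebo | First-stop difference | Approx. power, 47 per arm |
|---|---|---|
| 0% / 0% | 54.0 − 30.0 = 24.0 h | 97% |
| 10% / 10% | 51.3 − 28.5 = 22.8 h | 96% |
| 20% / 20% | 48.6 − 27.0 = 21.6 h | 95% |
| 30% / 30% | 45.9 − 25.5 = 20.4 h | 94% |
| 30% / 10% | 51.3 − 25.5 = 25.8 h | 99% |
| 10% / 30% | 45.9 − 28.5 = 17.4 h | 82% |

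The power column uses SDs of 28.2 to 29.9 h from simulated gamma-distributed times. In this model the benefit is overstated only if 15 r_active exceeds 27 r_placebo, that is, if active patients restart more than 1.8 times as often as placebo patients. If instead each restart adds the same number of hours in both arms, equal restart rates leave the difference unchanged.

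**3. Restarts when there is no true effect.** Set both final-stop means to 54 h, 47 per arm.

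- Equal shares (20% / 20%): expected difference 0, two-sided error 5.0%.
- 30% in one arm, 10% in the other: 54 × 0.95 − 54 × 0.85 = 5.4 h. With SD 29.6 h, SE = 29.6 × √(2/47) = 6.11 h, and 5.4/6.11 = 0.88. Two-sided rejection = 1 − Φ(1.96 − 0.88) + Φ(−1.96 − 0.88), about 14%, favouring whichever arm restarts more.

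**4. Death.** Read literally, a patient who dies within 30 h of starting study drug, with pressors stopped at that point, scores no worse than the mean projected for the active arm. The documents do not say how often this is expected. The protocol's Background does cite septic shock mortality of up to 45%, so it cannot be assumed rare.

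**5. Would a 24 h rule be enough?** Study drug runs for up to 4 days (96 h). A patient off pressors at 30 h, the projected active mean, has been off for 96 − 30 = 66 h by then, so a 24 h rule still records 30 h if pressors restart at 96 h. A final-stop rule, with a 24 h restart, records 96 + 24 = 120 h, which is 90 h later. The two definitions answer different questions, and late restarts need the second.

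**The case against.** The strongest defence is that the text never says first or any stop. The end-point's name speaks of independence, which fits a final or lasting stop at least as well as a brief pause. This stands: the definition is ambiguous rather than plainly wrong.

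A reader might infer more, namely that the rule overstates the benefit. The argument would be that the Background says "While corticosteroids decrease vasopressor dependency the effect on survival is less clear" and that hydrocortisone ends after at most 4 days, so the active arm should have more early stops and more later restarts. The documents do not support that. The sentence says nothing about restarts and fits fewer of them in the active arm equally well; no rebound is described and no rate is given. One can assume 10 to 30 percentage points more restarts in the active arm at 24 to 36 h each, which gives 0.1 × 24 = 2.4 h to 0.3 × 36 = 10.8 h, or 10% to 45% of the planned 24 h. With SD 30 h and 47 per arm, artefacts of 4.8, 7.2 and 10.8 h would be declared significant in about 12%, 21% and 41% of trials, against a nominal 5%. The arithmetic is right, but the direction is put in by hand. Reverse the assumption and the same hours favour placebo; make the rates equal and they vanish.

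Blinding is also a fair point. Only the pharmacist holds the allocation until the study is completed, so a rule can still be fixed blind. That shows the gap can be closed; it does not close it. Finally, 24 h is a convention, and a sustained-off rule alone gives no value to patients who die on pressors. Both are true, and the fix has to deal with the second.

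**Conclusion.** The point holds as an ambiguity with real consequences on a primary end-point. It does not hold as a demonstrated overstatement of benefit.

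Size and direction are unknown from the documents. Equal restart rates leave the difference unchanged or dilute it somewhat and do not inflate the error rate. Unequal rates can push false positives above 5% in either direction. The figures in the working rest on assumed restart shares, an assumed first stop at half the final time, two-sided testing and 47 per arm; they show sensitivity and do not predict this trial's bias. The absence of a requirement to be alive needs no assumption: it follows from the wording in both documents.

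**What to change.** Before unblinding, put the same text in the protocol and the SAP:

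- **Event.** For analysis, the end-point is reached at the start of the first period of at least 24 consecutive hours alive and off all vasopressors, derived from the hourly dose record.
- **Deaths.** Patients who die without reaching the event are ranked as the worst outcome. This commits the end-point to the Mann-Whitney comparison the plan already allows, since a t test has no value to use for them.
- **Sensitivity analysis.** Repeat the comparison using the final discontinuation in the index ICU stay, to catch restarts after study drug ends.
- **Recording window.** Confirm and state that hourly doses are recorded through the index ICU stay. If they are not, the sensitivity analysis cannot be done as described.

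The cost is a few lines of text and a derivation from a record the protocol already plans, subject to that check on the window. Measured times become slightly longer, and ranking deaths as worst makes the result partly a statement about survival, which the report should say. The 24 h period is a measurement convention and changes no patient care.

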***Hydrocortisone:*** Patients will be treated with hydrocortisone 50mg IV push every 6 hours for 4 days (or discontinued earlier if discharged from the ICU). Pharmacists will prepare hydrocortisone 50mg/1mL for the nurse in a 3mL syringe which will be labeled “Hydrocortisone 50mg or Placebo”. Hydrocortisone placebo will be provided as an identical 3mL syringe as 1mL of normal saline. Two doses of study medication will be prepared at a time.

***Thiamine:*** Intravenous thiamine will be given in a dose of 200mg q 12 hourly for 4 days (or discontinued earlier if discharged from the ICU). This will be placed in a 50mL bag of Normal Saline labeled “Thiamine 200mg or Placebo” and run over 30 minutes (100mL/hr) Placebo patients will receive a matching 50mL bag of Normal Saline. One dose will be prepared at a time.

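### Delta SOFA, a primary end-point, has no rule for death before day 4, and the protocol's SOFA timing does not settle the initial score or scoring after ICU discharge

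*Protocol*

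**What the plan says.** The Protocol (Primary end-point) and the SAP (Study end-points) use the same words: "Delta SOFA score, defined as the initial SOFA score minus the day 4 SOFA score". The Data analysis text in both names Student's t test, or the Mann-Whitney test for non-normal data. It gives no analysis population and no rule for death or a missing score. The Power Calculation raises the target from 94 to 140 for dropouts and for patients who need no vasopressor, but does not say how a dropout is analysed.

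Death is dealt with in a secondary end-point: "ICU free days is calculated as the number of days alive and out of the ICU to day 28".

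Protocol, Data Collection, puts SOFA on two clocks. The daily "score will be recorded for the first 4 treatment days". Also, "The SOFA scores is calculated 24 hours" "after admission to the ICU and daily thereafter". Neither clock is linked to the word 'initial'. The same section lists "Routine laboratory data for 4 days including", and urine output over the same span, with no ICU limit. Under Medication dosing, each study drug runs 4 days "or discontinued earlier if discharged from the ICU". The SAP adds nothing on SOFA timing.

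**The concern.** There are three gaps of unequal weight.

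- **Early death.** Whether a patient has a day-4 score depends on surviving to day 4, which treatment may affect. A comparison limited to patients with a score no longer rests on randomisation alone, and it ignores the worst outcome. An arm that loses its sickest patients early can look better on delta SOFA.
- **Initial score.** If it is taken after the first dose, part of any treatment effect is already in the baseline and is subtracted out.
- **ICU discharge.** If scoring stops at discharge, the patients who recover fastest also lose their day-4 score.

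All three affect one of the two primary end-points.

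**Working it through.** **The plan's own figure.** Inputs from the Power Calculation: change 4 versus 2, SD 3, alpha 0.05 (taken as two-sided), power 80%, 1:1 allocation assumed. Per arm, n = 2 × (1.960 + 0.842)² × (3/2)² = 2 × 7.85 × 2.25 = 35.3, so 36, or 72 in total (74 with the t distribution). The stated 94 is not reproduced. That is a separate matter. At 70 per arm, power = Φ(2 / (3 × √(2/70)) − 1.960) = Φ(1.98) = 0.98. With scores missing at random it is 0.96 at 10% missing and 0.91 at 30%, so lost numbers alone are not the problem.

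**Assumptions for the simulations (none is in the documents).** Initial SOFA mean 6, 8, 10 or 12, SD 3; integer scores held within 0-24; change 4 versus 2, SD 3; 70 per arm. Death before day 4 is unrelated to SOFA, or depends on initial or day-4 SOFA (logistic, slope 0.35 per point). The floor at 0 reduces the true difference from 2 to 1.76 at baseline 8.

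**Early deaths left out (2-15% per arm).** At baseline 8 the observed difference is 1.53-1.77 against 1.76, with power 89-96%. Over all baselines power is 82-97% and at most about 0.23 points are lost.

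**Wrong direction.** With no SOFA effect and deaths of 20% active versus 10% control, the survivors-only difference shifts by −0.04 to +0.23 points. Significance favouring the arm with more deaths occurs in 1.9-6.3% of trials (nominal 2.5%). With death ranked worst it is 0.1-0.5%.

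**Rule left open.** With no effect on SOFA or death and 5-15% deaths per arm, each single rule holds about 5%. Taking the better of survivors-only and death-worst gives 6.5-8.6%.

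**Initial score after dosing.** Inclusion Criteria require diagnosis within 12 hours of ICU admission. No passage gives the time to first dose. If that dose comes at hour h after admission, with h below 24, a 24-hour score falls 24 − h hours into treatment. Assume the effect builds evenly over 96 hours at baseline 8:

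- 12 hours in: 1.76 × (1 − 12/96) = 1.54
- 24 hours in: 1.76 × (1 − 24/96) = 1.32

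Power stays at 96% if patient spread shrinks in step, and falls to 88% or 76% if it does not. The 24-hour case needs a first dose at ICU admission, so it is an upper limit.

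**ICU discharge.** SOFA is recorded over treatment days, and treatment ends at ICU discharge, which suggests that scoring stops. Laboratory values and urine output run four days without that limit, which suggests that it continues. Data Collection lists no neurological item, so the listed data may not complete a ward score.

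**Covariate.** Complete data, equal variances, correlation 0.5 between initial and day-4 SOFA: the adjusted SD is 3 × √((1 + 0.5)/2) = 2.60, and power rises from 97.5% to 99.5%. If change is independent of the initial score there is no gain (96% against 96% at baseline 8). With death ranked worst, 10% deaths per arm and a day-4-on-initial slope of 0.5, Mann-Whitney on change has power 0.82 and ANCOVA on its ranks 0.90. Ranked day-4 SOFA as the outcome is less safe. Against Mann-Whitney on change it gave 0.72 versus 0.82 (10% deaths per arm) and 0.55 versus 0.68 (10% active, 5% control). It was about equal (0.84 versus 0.83) when death depended on day-4 SOFA at 10% per arm.

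**The case against.** The strongest reply is that early deaths may be few. The Exclusion criteria remove patients with care limitations or terminal disease, and the figures above show a small effect from deaths alone. This stands, and it limits the size of the point. It does not supply a rule, and the wrong-direction result does not depend on losing much power.

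The plan also allows Mann-Whitney, which could rank deaths worst. It could, but the text does not say so, and that test is chosen there for non-normality.

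A reader might infer that the documents are silent on the initial score and on scoring after discharge. They are not: Data Collection speaks to both, in terms that do not agree. The 24-hour wording might also mean a score built from values gathered over the first 24 hours; the text does not say which values count.

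A reader might take the 40.4% and 8.5% mortality in the Background as a sign of large early imbalance. Those are hospital deaths in a before-after study, not deaths by day 4 in a randomised trial.

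Larger effects can be produced by assuming that discharged patients lack scores. At baseline 8, with 29-46% unscored, power is 58-84%. This needs an assumed discharge threshold (day-4 SOFA at or below 1-3) and a reading that the text leaves open, so it is not relied on here.

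**Conclusion.** The point holds in a limited form. The absence of a rule for death before day 4 is plain in both documents, and as written the t test compares survivors only. The effect on the estimate and power is modest under assumed early deaths of 2-15% per arm. The more serious consequence is a test that can favour the arm with more deaths (about 2-6% against 2.5%, under 1% with death ranked worst, at assumed deaths of 20% versus 10%). The initial-score and discharge points are conflicting wording. A post-dose baseline dilutes the effect and favours neither arm.

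The documents do not support a claim that early deaths invalidate the end-point, or that covariate adjustment is free whatever outcome is modelled. Confidence is high in the omission and moderate in its size, since every death rate and baseline is assumed. This should be fixed, but it is not fatal.

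**What to change.** Amend the SAP before the allocation log is opened. Data Collection keeps that log with the pharmacist until the study is completed, so the rule can be set blind.

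1. Define initial SOFA from the last values before the first dose of study drug.
2. Analyse all randomised patients on delta SOFA, ranking death before day 4 below every survivor. Keep the observed-case change as a sensitivity analysis, and report missing day-4 scores by arm and reason.
3. Keep the change score as the outcome and add initial SOFA as a covariate. ANCOVA on the ranks of change suits the main analysis, since a death has no numeric change; ANCOVA on change itself suits the observed cases. Do not substitute ranked day-4 SOFA.
4. Reconcile the Data Collection wording so that day-4 SOFA is scored whether or not the patient is still in the ICU. Add the neurological component to the listed data.

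**Cost.** This needs SAP text, a pre-dose score, and day-4 components collected on the ward. The end-point becomes a composite with death, although mortality is already secondary. At baseline 8, with 4 versus 2 and 70 per arm, simulated power with death ranked worst and the covariate is about 82-96% at 10% deaths per arm. It is about 69-94% at 10% active versus 5% control, so it can fall below the stated 80%. Part of that loss is intended, because a SOFA gain alongside more early deaths should be harder to declare.
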